4.6.3. Other Clinically Relevant Information

Additional details concerning safety observations from clinical studies and for which a causal association has not been established or which are of minimal clinical significance may be found in the Investigator's Brochure. Please refer to Section 6: 'Summary of Data and Guidance for the Investigator'.

Adverse Events of Special Interest

Seizure

Three cases of seizures have occurred in the cabotegravir programme cumulatively through 01 October 2016. Two of the cases occurred in HIV uninfected subjects with a prior history of seizure and one case involved a subject in study 200056 [GlaxoSmithKline Document Number [2013N168152_04](#), 200056] with circumstantial and anecdotal evidence of illicit drug use. Overall, there is not convincing evidence that

cabotegravir exposure may be causally associated with seizure or with reduction of seizure threshold, due to the low frequency of reports, the confounders present in the cases received to date, and lack of any pre-clinical signal or identified plausible mechanism. However seizure and seizure-like events are considered as AEs of special interest for close monitoring in all studies. Subjects with recent history of, or recent treatment for seizure will be excluded from study participation.

4.6.4. Benefit Assessment

Subjects participating in the study will not receive any clinical benefit, but will be compensated for their time and participation.

4.6.5. Overall Benefit: Risk Conclusion

Taking into account the measures taken to minimize risk to subjects participating in this study, the potential risks identified in association with CAB and RBT are justified by the anticipated benefits that may be afforded to subjects with HIV and to those healthy subjects who may benefit from CAB as a preventative agent for acquisition of HIV.

5. SELECTION OF STUDY POPULATION AND WITHDRAWAL CRITERIA

Specific information regarding warnings, precautions, contraindications, adverse events, and other pertinent information on the GlaxoSmithKline (GSK) investigational product or other study treatment that may impact subject *eligibility* is provided in the IB for cabotegravir (CAB) and the Product Monograph for Mycobutin Capsules (rifabutin capsules).

Deviations from inclusion and exclusion criteria are not allowed because they can potentially jeopardize the scientific integrity of the study, regulatory acceptability or subject safety. Therefore, adherence to the criteria as specified in the protocol is essential.

5.1. Inclusion Criteria

Specific information regarding warnings, precautions, contraindications, adverse events, and other pertinent information on the ViiV Healthcare investigational product or other study treatment that may impact subject eligibility is provided in the Investigators Brochure (IB).

A subject will be eligible for inclusion in this study only if all of the following criteria apply:

AGE

1. Males and females between 18 and 65 years of age inclusive, at the time of signing the informed consent.

TYPE OF SUBJECT AND DIAGNOSIS INCLUDING DISEASE SEVERITY

2. Healthy as determined by the investigator or medically qualified designee based on a medical evaluation including medical history, physical examination, laboratory tests and cardiac monitoring.
3. A subject with a clinical abnormality or laboratory parameter(s) which is/are not specifically listed in the inclusion or exclusion criteria, outside the reference range for the population being studied may be included only if the investigator in consultation with the Medical Monitor agree and document that the finding is unlikely to introduce additional risk factors and will not interfere with the study procedures. Additionally, laboratory assessments that are specifically listed in the inclusion or exclusion criteria and are outside of the reference range can be repeated once during the screening period.

WEIGHT

4. Body weight ≥ 50 kg and body mass index (BMI) within the range 18.5 – 31.0 kg/m² (inclusive).

SEX

5. Male or female

A female subject is eligible to participate if she is not pregnant (as confirmed by a negative serum human chorionic gonadotrophin (hCG) test), not lactating, and at least one of the following conditions applies:

- a. Non-reproductive potential defined as:
 - Pre-menopausal with one of the following:
 - Documented tubal ligation
 - Documented hysteroscopic tubal occlusion procedure with follow-up confirmation of bilateral tubal occlusion
 - Hysterectomy
 - Documented Bilateral Oophorectomy
 - Postmenopausal defined as 12 months of spontaneous amenorrhea [in questionable cases a blood sample with simultaneous follicle stimulating hormone (FSH) and estradiol levels consistent with menopause FSH: >40 MIU/mL and estradiol <40 pg/mL (<147 pmol/L) is confirmatory].
- b. Reproductive potential and agrees to follow one of the options listed in the Modified List of Highly Effective Methods for Avoiding Pregnancy in Females of Reproductive Potential (FRP) (see [Appendix 5](#): Modified List of Highly Effective Methods for Avoiding Pregnancy in FRP and Collection of Pregnancy

Information) from 30 days prior to the first dose of study medication until the completion of the follow-up visit.

The investigator is responsible for ensuring that subjects understand how to properly use these methods of contraception.

INFORMED CONSENT

6. Capable of giving signed informed consent as described in Section 10.2 which includes compliance with the requirements and restrictions listed in the consent form and in this protocol.

ACCEPTABLE LIVER CHEMISTRY AND HEMATOLOGY CRITERIA

7. ALT, alkaline phosphatase and bilirubin $\leq 1 \times \text{ULN}$ (isolated bilirubin $> 1.5 \times \text{ULN}$ is acceptable if bilirubin is fractionated and direct bilirubin $< 35\%$).
8. White blood cell count and absolute neutrophil count in the normal range.

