5.2. Exclusion Criteria

A subject will not be eligible for inclusion in this study if any of the following criteria apply:

CONCURRENT CONDITIONS/MEDICAL HISTORY (INCLUDES LIVER FUNCTION AND QTc INTERVAL)

1. Current or chronic history of liver disease, or known hepatic or biliary abnormalities (with the exception of Gilbert's syndrome or asymptomatic gallstones).
2. History of clinically significant cardiovascular disease including:
 - a. Exclusion criteria for screening ECG (a single repeat is allowed for eligibility determination):

	Males	Females
Heart rate	<45 and >100 beats per minute	<50 and >100 beats per minute
QRS duration	>120 msec	
QTc interval (F)	>450 msec	

- b. Evidence of previous myocardial infarction (pathologic Q waves, S-T segment changes (except early repolarization)).
- c. History/evidence of symptomatic arrhythmia, angina/ischemia, coronary artery bypass grafting (CABG) surgery or percutaneous transluminal coronary angioplasty (PCTA) or any clinically significant cardiac disease.
- d. Conduction abnormality (including but not specific to left or right complete bundle branch block, AV block [2nd degree (type II) or higher], Wolf Parkinson White [WPW] syndrome) which in the opinion of the principal Investigator and Viiv Medical Monitor, will interfere with the safety for the individual subject.

- e. Sinus pauses >3 seconds.
- f. Any significant arrhythmia which, in the opinion of the principal Investigator and Viiv Medical Monitor, will interfere with the safety for the individual subject.
- g. Non-sustained (≥ 3 consecutive ventricular ectopic beats) or sustained ventricular tachycardia.

NOTES:

- The QTc is the QT interval corrected for heart rate according to Fridericia's formula (QTcF), machine-read or manually over-read.
3. History of inflammatory bowel disease.
 4. History of cholecystectomy or other gastrointestinal surgery (except appendectomy more than three months prior to study).
 5. History of peptic ulceration or pancreatitis within the preceding 6 months of screening.
 6. Participants determined by the Investigator to have a high risk of seizures, including participants with an unstable or poorly controlled seizure disorder. A participant with a prior history of seizure may be considered for enrolment if the Investigator believes the risk of seizure recurrence is low. All cases of prior seizure history should be discussed with the Medical Monitor prior to enrolment.
 7. Current or past history of uveitis.

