 8. Any other medical condition which, in the judgment of the investigator and medical monitor, could jeopardize the safety of the subject or the integrity of the data derived from that subject. This includes but is not limited to any pre-existing condition that interferes with normal gastrointestinal anatomy or motility that could interfere with the absorption, metabolism, and/or excretion of the study drug.

CONCOMITANT MEDICATIONS

9. Unable to refrain from the use of prescription or non-prescription drugs, including vitamins, herbal and dietary supplements (including St John's Wort) within 7 days (or 14 days if the drug is a potential enzyme inducer) or 5 half-lives (whichever is longer) prior to the first dose of study medication, unless in the opinion of the Investigator and Viiv Medical Monitor the medication will not interfere with the study procedures or compromise subject safety. See Section 6.10.2 for concomitant medications that are prohibited for this study.

RELEVANT HABITS

10. History of regular alcohol consumption within 6 months of the study defined as an average weekly intake of >14 drinks. One drink is equivalent to 12 g of alcohol, 12 ounces (360 mL) of beer, 5 ounces (150 mL) of wine or 1.5 ounces (45 mL) of 80 proof distilled spirits.
11. A history of regular use of tobacco, or nicotine-containing products within 30 days prior to screening.

CONTRAINDICATIONS

12. History of sensitivity to any of the study medications, or components thereof or a history of drug or other allergy that, in the opinion of the investigator or Medical Monitor, contraindicates their participation.

DIAGNOSTIC ASSESSMENTS AND OTHER CRITERIA

13. Presence of Hepatitis B surface antigen (HBsAg) positivity at screening or within 3 months prior to first dose of study treatment. Positive Hepatitis B core antibody (HBcAb) with negative hepatitis B surface antibody should also be excluded.
14. Positive Hepatitis C antibody test.
15. A positive pre-study drug/alcohol screen.
16. A positive test for HIV antibody.
17. A positive QuantiFERON Gold test or clinical evidence of tuberculosis (TB) infection.
18. Where participation in the study would result in donation of blood or blood products in excess of 500 mL within a 56 day period.

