Injection Site Pruritus	Itching localized to the injection site that is relieved spontaneously or in < 48 hours of treatment	Itching beyond the injection site that is not generalized OR Itching localized to the injection site requiring \geq 48 hours treatment	Generalized itching causing inability to perform usual social & functional activities	NA
LABORATORY VALUES Chemistries				
Acidosis	NA	pH \geq 7.3 to < LLN	pH < 7.3 without life-threatening consequences	pH < 7.3 with life-threatening consequences
Albumin, Low (g/dL; g/L)	3.0 to < LLN 30 to < LLN	\geq 2.0 to < 3.0 \geq 20 to < 30	< 2.0 < 20	NA
Alkaline Phosphatase, High	1.25 to < 2.5 x ULN	2.5 to < 5.0 x ULN	5.0 to < 10.0 x ULN	\geq 10.0 x ULN
Alkalosis	NA	pH > ULN to \leq 7.5	pH > 7.5 without life-threatening consequences	pH > 7.5 with life-threatening consequences
ALT or SGPT, High Report only one	1.25 to < 2.5 x ULN	2.5 to < 5.0 x ULN	5.0 to < 10.0 x ULN	\geq 10.0 x ULN
Amylase (Pancreatic) or Amylase (Total), High Report only one	1.1 to < 1.5 x ULN	1.5 to < 3.0 x ULN	3.0 to < 5.0 x ULN	\geq 5.0 x ULN
AST or SGOT, High Report only one	1.25 to < 2.5 x ULN	2.5 to < 5.0 x ULN	5.0 to < 10.0 x ULN	\geq 10.0 x ULN
Bicarbonate, Low (mEq/L; mmol/L)	16.0 to < LLN 16.0 to < LLN	11.0 to < 16.0 11.0 to < 16.0	8.0 to < 11.0 8.0 to < 11.0	< 8.0 < 8.0
Bilirubin Direct Bilirubin ¹⁴ , High > 28 days of age	NA	NA	> ULN	> ULN with life-threatening consequences (e.g., signs and symptoms of liver failure)
\leq 28 days of age	ULN to \leq 1 mg/dL	> 1 to \leq 1.5 mg/dL	> 1.5 to \leq 2 mg/dL	> 2 mg/dL
Total Bilirubin, High > 28 days of age	1.1 to < 1.6 x ULN	1.6 to < 2.6 x ULN	2.6 to < 5.0 x ULN	\geq 5.0 x ULN
\leq 28 days of age	Total Bilirubin for Term and Preterm Neonates	Total Bilirubin for Term and Preterm Neonates	Total Bilirubin for Term and Preterm Neonates	Total Bilirubin for Term and Preterm Neonates

PARAMETER	GRADE 1 MILD	GRADE 2 MODERATE	GRADE 3 SEVERE	GRADE 4 POTENTIALLY LIFE-THREATENING
Calcium, High (mg/dL; mmol/L) ≥ 7 days of age	10.6 to < 11.5 2.65 to < 2.88	11.5 to < 12.5 2.88 to < 3.13	12.5 to < 13.5 3.13 to < 3.38	≥ 13.5 ≥ 3.38
< 7 days of age	11.5 to < 12.4 2.88 to < 3.10	12.4 to < 12.9 3.10 to < 3.23	12.9 to < 13.5 3.23 to < 3.38	≥ 13.5 ≥ 3.38
Calcium (Ionized), High (mg/dL; mmol/L)	> ULN to < 6.0 > ULN to < 1.5	6.0 to < 6.4 1.5 to < 1.6	6.4 to < 7.2 1.6 to < 1.8	≥ 7.2 ≥ 1.8

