12.7. Appendix 7: Toxicity Management

ANEMIA

Grade 1 (mild) hemoglobin decrease:

Any hemoglobin decrease meeting the definition of Grade 1 must be repeated with the following additional tests:

1. peripheral blood smear
2. indirect bilirubin (abnormal if increased >50% from baseline)
3. haptoglobin (abnormal if ≤ 25 mg/dL)
4. reticulocyte count (abnormal if $\geq 4\%$)

If the additional tests are within the normal range, subjects may continue study medication. If one or more of the additional tests is abnormal or suggestive of hemolytic anemia as specified above, subjects will permanently discontinue study medication and be withdrawn from the trial. Subjects should be followed up until resolution of anemia.

Grade 2 (moderate) hemoglobin decrease:

Any hemoglobin decrease meeting the definition of Grade 2 must be repeated with the following additional tests:

5. peripheral blood smear
6. indirect bilirubin (abnormal if increased >50% from baseline)
7. haptoglobin (abnormal if ≤ 25 mg/dL)
8. reticulocyte count (abnormal if $\geq 4\%$)

If the additional tests are within the normal range, subjects may continue study medication. If one or more of the additional tests is abnormal or suggestive of hemolytic anemia as specified above, subjects will permanently discontinue study medication and be withdrawn from the trial. Consultation with a Hematologist should be considered. Subjects should be followed up until resolution of anemia.

Grade 3 (severe) or Grade 4 (potentially life threatening) hemoglobin decrease:

Any hemoglobin decrease meeting the definition of Grade 3 or 4 must be repeated with the following additional tests:

9. peripheral blood smear
10. indirect bilirubin
11. haptoglobin
12. reticulocyte count

Subjects will permanently discontinue study medication and be withdrawn from the trial. Consultation with a Hematologist should be considered. Subjects should be followed up until resolution of anemia.

TOTAL BILIRUBIN ELEVATION

Grade 1 (mild) bilirubin elevation (1.1 - 1.5 times ULN) or Grade 2 (moderate - 1.6-2.5 times ULN):

Any bilirubin value above the upper limit of normal must be repeated and fractionated (direct and indirect bilirubin). Subjects may continue study medication. Subjects should be followed up until resolution (return to baseline) of elevation.

Grade 3 (severe – 2.6-5.0 times ULN) or 4 (life-threatening - > 5.0 times ULN) bilirubin elevation:

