Any bilirubin value above the upper limit of normal must be repeated and fractionated (direct and indirect bilirubin). Subjects will permanently discontinue study medication and be withdrawn from the trial. Subjects should be followed up until resolution (return to baseline) of bilirubin elevation.

AST AND ALT ELEVATION

See [Appendix 2](#).

RASH

Grade 1 rash (Localized macular rash):

Subjects with Grade 1 rash should be evaluated by the Investigator immediately. A dermatologist may be consulted and a biopsy may be obtained if recommended by the dermatologist. The study drug should be permanently discontinued if the following signs or symptoms are noted at any time:

13. Temperature > 38.5°C
14. Lymphadenopathy
15. Pharyngitis
16. Any indication of internal organ involvement (hepatitis, nephritis)

In the absence of the above signs or symptoms, subjects with Grade 1 rash may continue the study drug at the discretion of the Investigator. The subject should be advised to contact the Investigator immediately if there is any worsening of the rash, if any systemic signs or symptoms worsen, or if mucosal ulceration develops. If the rash is considered to be most likely due to concomitant illness or non-study medication, standard management, including discontinuation of the likely causative agent, should be undertaken. If no other causative factor is found after clinical evaluation, the subject may be treated symptomatically until the rash resolves. Antihistamines, topical corticosteroids or

antipruritic agents may be prescribed. The subject should remain on the study to be followed for safety and PK as outlined in Section 7.3 and Section 7.4

Grade 2 rash (Diffuse macular, maculopapular, or morbilliform rash OR Target lesions):

Subjects with Grade 2 rash should be evaluated by the Investigator immediately. Digital photographs should be obtained. A dermatologist may be consulted and a biopsy may be obtained if recommended by the dermatologist. The study drug should be permanently discontinued if the following signs or symptoms are noted at any time:

17. Temperature > 38.5°C
18. Lymphadenopathy
19. Pharyngitis
20. Any indication of internal organ involvement (hepatitis, nephritis)

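### Inclusion criterion 7 rejects isolated bilirubin of >1.0 to 1.5×ULN but accepts >1.5×ULN without a ceiling, so it can admit a volunteer who already meets the Appendix 7 withdrawal threshold

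*Protocol*

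**What the plan says.** **Entry.** Protocol 5.1, criterion 7, limits ALT, alkaline phosphatase and bilirubin to 1×ULN. Its exception is that isolated bilirubin above 1.5×ULN "is acceptable if bilirubin is fractionated and direct bilirubin" is below 35%. No maximum is given. Exclusion 1 (5.2) bars liver and biliary disease "with the exception of Gilbert's syndrome or asymptomatic gallstones", again with no bilirubin limit.

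**On treatment.** Appendix 7 lets subjects continue at Grade 1 and up to "Grade 2 (moderate - 1.6-2.5 times ULN"). From "Grade 3 (severe – 2.6-5.0 times ULN") upward, the value is repeated and fractionated, and the instruction is: "Subjects will permanently discontinue study medication and be withdrawn from the trial". The fractionation result plays no part in that action. Baseline appears only as the point at which follow-up ends.

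**Grading.** Appendix 6 puts the same cut at 2.6×ULN: Grade 2 total bilirubin is "1.6 to < 2.6 x ULN".

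**Discretion.** Section 5 disallows deviations from the entry criteria, and Section 7 disallows waivers except for immediate safety concerns. The discretion in inclusion 3 covers only laboratory parameters that the criteria do not list. Bilirubin is listed, so an out-of-range value may only be repeated once.

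**The concern.** The sentence has two faults. The acceptable range has a hole in it: mild elevation is refused while larger elevation is accepted. It also has no top, so entry overlaps with a mandatory withdrawal rule. Someone whose bilirubin has not changed since screening could be enrolled, dosed and then withdrawn for that same value.

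What is at stake is the volunteer rather than the analysis. Section 4.6.4 states that subjects receive no clinical benefit, so dosing someone whose withdrawal can be foreseen at screening should be avoided.

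**Working it through.** **1. Compare the two rules.** Take isolated total bilirubin with direct <35% and other liver tests within limits. Eligible now means ≤1 or >1.5×ULN. The Appendix 7 stop applies at ≥2.6×ULN.

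| Bilirubin (×ULN) | Eligible now | Meets Appendix 7 stop | Eligible with a 2.0 cap |
|---|---|---|---|
| 1.0 | yes | no | yes |
| 1.2 | no | no | yes |
| 1.5 | no | no | yes |
| 2.0 | yes | no | yes |
| 2.5 | yes | no | no |
| 2.6 | yes | **yes** | no |
| 3.0 | yes | **yes** | no |
| 6.0 | yes | **yes** | no |

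The overlap is every isolated value of 2.6×ULN or more with direct <35%. The hole is >1.0 to 1.5×ULN. Capping at 2.0 and starting the exception at 1 removes both.

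**2. Does the stop depend on baseline?** The documents state a baseline or fraction condition where they want one. The Appendix 7 anemia rule uses "indirect bilirubin (abnormal if increased >50% from baseline"). Appendix 6 grades creatinine on multiples of ULN or on a rise above baseline. The SAE rule in Appendix 2 counts bilirubin only together with ALT and with more than 35% direct. The Appendix 7 Grade 3–4 bilirubin stop carries no such condition.

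**3. Timing.** The SAP Time and Events table places safety laboratory tests at screening, Days −1, 13 and 27, and follow-up. These days are read from a badly extracted row, but its spacing from Day −1 on matches the unit-admission row (Days −1, 13, 27). The first test on treatment is therefore Day 13, preceded by 12 cabotegravir doses (Days 1–12).

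**4. Headroom under a cap.** Rise needed to reach the stop = 2.6/cap − 1.
- Cap 2.5: 2.6/2.5 − 1 = 4%
- Cap 2.0: 2.6/2.0 − 1 = 30%

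**5. Precision.** Half-width of the 90% CI on the log scale = t(0.95, n−1) × √ln(1+CVw²) × √(2/n). With the plan's CVw of 11.4% and n = 12 this gives 8.3%, which reproduces Section 9.2.1. Going from 15 to 14 evaluable subjects moves it from 7.3% to 7.6%. The plan already expects 15 × 20% = 3 losses, and Section 4.3 permits replacement.

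**The case against.** The strongest reply is that Appendix 7 manages toxicity, follows elevations until they return to baseline, and so is aimed at a rise. A subject unchanged from 2.7×ULN has nothing to resolve. Appendix 4 likewise leaves non-worsening fluctuation of a pre-existing condition outside the AE definition, and the SAP's summary and listing of Grade 2 or higher laboratory abnormalities are restricted to treatment-emergent ones. This makes a baseline-relative intention plausible. It does not change the trigger: those passages govern AE recording and reporting, while the stop is written on the value alone.

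Investigator judgment also reduces the likelihood. Inclusion 2 requires the subject to be judged healthy, and exclusion 8 allows a condition to exclude if it "could jeopardize the safety of the subject or the integrity of the data derived from that subject". Both can keep a very high value out, but neither sets a limit. The liver stopping algorithm (Figure 1, Section 5.4.2) is not visible in the copy examined. The visible Appendix 2 table stops on ALT ≥3×ULN and does not override Appendix 7.

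A reader might infer that the Day −1 value already forces withdrawal. That is doubtful, because Appendix 7 speaks of discontinuing study medication and none has been given by then. A reader might also take 12 doses as the most that could be given needlessly. It is only the number before the Day 13 visit; laboratory turnaround is not stated, so further doses could follow.

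**Conclusion.** Criterion 7 is wrong as written, and the matter is minor. The hole at >1.0 to 1.5×ULN and the missing ceiling are plain from the text. The hole looks like a drafting slip, and its only effect is to screen out some volunteers. Withdrawal of a subject with a stable value of 2.6×ULN or more follows from a literal reading of Appendix 7. It also requires that such a subject is judged healthy and is not turned away on the Day −1 result.

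The case is probably rare; no frequency is given. It would be wrong to infer a threat to the trial's conclusions: no estimate changes, and the loss of one subject is immaterial to precision. The gain is avoiding foreseeable withdrawal and needless dosing of healthy volunteers.

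**What to change.** Reword criterion 7 as: ALT and alkaline phosphatase ≤1×ULN; bilirubin ≤1×ULN, or isolated bilirubin >1 to 2.0×ULN if fractionated and direct bilirubin <35%. Leave the Appendix 7 stop as it is.

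A cap of 2.5×ULN, the top of Appendix 7 Grade 2, is the bare maximum that avoids withdrawal on an unchanged value, but a trivial fluctuation would still cross the stop. A cap of 2.0×ULN leaves room for ordinary variation. Adding a baseline or direct-fraction condition to Appendix 7 would also reconcile the texts, but it would loosen an on-treatment safety rule.

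The cost is one sentence in an amendment, with no added procedure. A few Gilbert's volunteers above 2.0×ULN are screened out. Those at >1.0 to 1.5×ULN with direct <35% become eligible, at lower values than the criterion already accepts.
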